1
2
3
4
5
6
7
8
9
10
11
12
13
14
15
16
17
18
19
20

**INTERMITTENT EXOTROPIA STUDY 5
(IXT5)**

**A Randomized Clinical Trial of Overminus Spectacle
Therapy for Intermittent Exotropia**

STATISTICAL ANALYSIS PLAN

**Version 2.2
February 25, 2021**

Based on Protocol Version 3.0 (November 22, 2019)

21 Revision History

VERSION NUMBER		AUTHOR	APPROVER	EFFECTIVE DATE	REVISION DESCRIPTION (INCLUDING SECTIONS REVISED)
SAP	Protocol				
1.0	V2.0 (Nov 16, 2016)	[name]	[name]	April 2, 2018	Initial version (Completed prior to first DSMC review of study data)
1.1	V2.0 (Nov 16, 2016)	[name]			
Section 4: To reflect the stated time-to-event analysis, changed name of deterioration outcomes to be “deterioration by” the 12-month and 18-month timepoints instead of “deterioration at” these timepoints,
 
Section 5.1: On outcome evaluating “no spontaneous tropia,” added acknowledgement that some participants may have met this criteria at baseline if they had a baseline control score of 2 or better (≤ 2) and did not have a spontaneous tropia at any time during the baseline visit at distance or at near.
 
Section 7.4: The comparison of refractive error between treatment groups will be performed at the 12-month visit only, so removed erroneous reference to an 18-month comparison.
 
Section 7.6: Added this new section describing tabulations on the IXT Symptom Survey.
 
Section 8.1: Added accommodative convergence/accommodation (AC/A) ratio as a baseline subgroup factor of interest. Also added a paragraph on the rationale for each baseline subgroup factor, and expected direction of effect for some of the factors.
 
Section 9.2: On the assessment of esodeviation, changed to assess “esodeviation by PACT” instead of “tropia by SPCT.”

2.0	V3.0 (Nov 22, 2019)	[name]	[name]	March 16, 2020	
Re-ordered analyses and created new headings throughout SAP.
 
Section 1.0: Clarified that all references to refractive error refer to refractive error in the more myopic eye.
 
Section 2.1: Edited to explain why ADHD will not be included in primary analysis.

					
Section 2.1.7: Added sensitivity analysis #5 that will include additional adjustment factors.
 
Section 2.1.9: Addressed how imputation will be handled under Protocol Amendment II for participants who missed certain visits.
 
Section 2.2: Explained that analysis will be repeated in a cohort limited to those who were prescribed weaning before Protocol Amendment II.
 
Section 2.3: Revised to say that effect of weaning will only be calculated in the overminus group and will not use ANCOVA but rather a t-test or Wilcoxon depending on normality of distribution. Also edited to say that the analysis will be limited to those who were prescribed weaning, and deleted part about Bonferroni correction as it will not be done here. Also added paragraph on calculation of the retention of 12-month treatment effect at 18 months.
 
Section 3.1: Edited to say that treatment groups will be compared using a Z-test as long as one of the proportions is between 0.05 and 0.95. Edited adjustment factors, deleting distance PACT and leaving only baseline factors of the deterioration clinical outcomes (stereo and control). Added paragraph on how proportional hazards assumption will be checked.
 
Section 3.2: Edited to say that cause-specific deterioration will be calculated only if overall deterioration is significant. Revised adjustment factors as in Section 3.1. Explained that alpha will be split between time points and gatekeeping strategy will be used. Stated that participants with nil stereo at baseline will be excluded.
 
Deleted sensitivity analysis on deterioration outcome (originally Section 4.3).
 
Section 4: Stated what statistics will be tabulated/calculated for all outcomes.

--	--	--	--	--	---

					
Explained that FDR multiplicity adjustment will be divided into 2 parts.
 
Section 4.1.1: Revised how “no spontaneous tropia” will be defined (ie just by control score)
 
Section 4.1.6: Deleted sentence about imputed data being used, as the observed data will be used here.
 
Section 4.1.7: Added section about Axial Length, which was added with Protocol Amendment II.
 
Section 4.1.8: Added section about additional ocular biometric parameters, which were added with Protocol Amendment II.
 
Section 4.2.1: Edited to state that 18-month subgroup analyses will be done only if there is an overall treatment group effect at 18 months. Redefined ranges for categories within baseline distance control subgroup and baseline refractive error subgroup. Edited how p-value will be calculated and interpreted. Table of summary of subgroups and expected directions of effect modification was added. Deleted paragraph about F-statistics. Included sentence about Forest plots that will be generated.
 
Section 4.2.2: Deleted paragraph about analysis on baseline distance control subgroup of 3 to <5 points. Added paragraph about analysis on mean distance control at 18 months according to prescribed weaning status.
 
Section 4.3.1: Added sentences about post-hoc risk ratio calculation of myopia progression for the overminus vs non-overminus group, both overall and in refractive error subgroups.
 
Section 4.3.2: Corrected esotropia to esodeviation and SPCT to PACT.
 
Originally Section 9.4: Deleted paragraph about Adverse Symptoms, as it was already being addressed in IXTQ section.

--	--	--	--	--	---

					Added sections on extension study.
2.1	V3.0 (Nov 22, 2019)	[name]		June 10, 2020	Revised per Leads' comments: Clarifications to study design and purpose; corrections to description of spectacle prescribing criteria.
2.2	V3.0 (Nov 22, 2019)	[name] [name]		February 25, 2021	
Updated analysis windows for 24- and 36-month visits.
 
 Shortened the lower limit of the 24-month visit window from ≤ 18 months to ≤ 21 months. Extended upper limit of 36-month visit analysis window from ≤ 36 months to ≤ 48 months 
Added sensitivity analysis of limiting primary analysis to visits completed within protocol window.
 
Added sensitivity analysis of limiting primary analysis to participants who were not treatment crossovers.
 
Added tabulation of outcomes by baseline SER subgroups to Section 5.5.
 
Added calculation of correlation coefficients for biometric measures with 24/36mo SER to Section 5.3.

22

[name]
Digitally signed by [name]
Date: 2021.02.25 12:22:33 -05'00'

[name], Statistician

[name]
I am signing this document
2021-03-02 08:27-05:00

[name], Epidemiologist

[name]
I am digitally signing this document
2021-02-25 13:58-05:00

[name], Senior Statistician

[name]
Digitally signed by [name]
DN: cn=[name], o, ou,
email=[contact], c=US
Date: 2021.03.04 18:26:14 -08'00'

[name], Protocol Co-Chair

[name]
Digitally signed by [name]
Date: 2021.03.07 22:33:11 -05'00'

[name], Protocol Co-Chair

[name]
Digitally signed by [name]
Date: 2021.03.04 13:14:41 -08'00'

[name],
PEDIG Network Co-Chair

[name] - ([name])
Digitally signed by [name] - ([name])
Date: 2021.02.25 10:15:17 -07'00'

[name],
PEDIG Network Co-Chair

23 **1. Design and Purpose of IXT5 Study**

24 The objectives of the IXT5 study are to determine the long-term on-treatment effect of
25 overminus treatment on distance IXT control score and the off-treatment effect of
26 overminus treatment on distance IXT control score following weaning and 3 months off
27 treatment. The participants will be randomly (1:1) assigned to the following treatment
28 groups:

- 29 • Overminus Group (-2.50D over the cycloplegic refraction for 12 months, -1.25D
30 over the cycloplegic refraction for 3 months, non-overminus correction for 3
31 months) Note that Protocol Amendment #2 (11/22/19) discontinued overminus
32 lenses.
- 33 • Non-overminus Group [spectacles that fully corrected the astigmatism and
34 anisometropia based on the cycloplegic refraction. The sphere power was based
35 on SE in the least hyperopic eye as follows: 1) full correction for SE myopia, 2)
36 sphere power that resulted in a plano SE lens (with symmetrical reduction in the
37 most hyperopic eye, if needed).

38
39 Note: any mention of refractive error from this point on will refer to refractive error in the
40 most myopic eye at baseline; this is because treatment was prescribed based on this eye
41 and eligibility criteria, so this is the eye that will be used for any analyses involving
42 refractive error.

43
44 **2. Objective I: Effect of Overminus Lenses on Distance Control**

45
46 **2.1 Primary Analysis – Efficacy of Overminus Treatment (12 Months, On-
47 Treatment)**

48 The primary analysis will be a two-sided comparison of mean 12-month control of the
49 distance exodeviation (mean of 3 measurements) between the treatment groups using an
50 analysis of covariance (ANCOVA) model which adjusts for the following baseline
51 factors to account for potential residual confounding: distance control, distance PACT,
52 age, and refractive error (in the most myopic eye at baseline). The ANCOVA model will
53 test the hypothesis that the treatment effect is different from zero (superiority hypothesis)
54 using a type I error rate of 5%. The treatment group difference (overminus – non-
55 overminus) and corresponding 95% confidence interval and p-value will be calculated.
56 While use of ADHD medication was specified in the protocol as a baseline adjustment
57 factor, this information was not collected at baseline due to an oversight. Therefore, this
58 will not be one of the adjustment factors in the model.

59
60 **2.1.1. Principles to be Followed in Primary Analysis**

61 Model assumptions for the ANCOVA will be assessed, including linearity of the
62 adjustment covariates (baseline distance control, distance PACT, age, and refractive
63 error), normal distribution and equal variance across the treatment groups. The linearity
64 assumption of the baseline covariates will be evaluated using descriptive scatterplots and
65 by categorizing each of the baseline factors in the model to check for approximate
66 linearity of the coefficients across ordered categories. A baseline covariate will be
67 included as a continuous variable in the model if the assumptions for linearity are met for
68 that covariate; otherwise, the baseline covariate will be categorized.

69
70
71
72
73
74
75
76
77
78
79
80
81
82
83
84
85
86
87
88
89
90
91
92
93
94
95
96
97
98
99
100
101
102
103
104
105
106
107
108
109
110
111
112
113
114

The 12-month distance control score for analysis for each participant is the mean of the 3 control assessments completed at that visit. When the protocol-specified three measures of control are not performed at the outcome exam, the mean of two measures will be used for analysis if only 2 distance control measures are completed; the single distance control score will be used for analysis if only 1 assessment of control is completed.

The primary analysis will follow a modified intention-to-treat principle, with all participants analyzed according to their randomized treatment group and with the following stipulations:

- Participants who are treatment crossovers (non-overminus group participants who are prescribed overminus; overminus group participants who have overminus spectacles formally discontinued before 12 months) will have their observed 12-month data analyzed provided they complete at least one distance control assessment at the 12-month outcome exam; otherwise, their mean distance control score will be imputed using multiple imputation.
- Participants who are prescribed IXT treatment other than overminus or non-overminus spectacles (e.g., surgery, vision therapy, patching) will have their mean distance control score imputed using multiple imputation, regardless of whether any control testing is completed at the 12-month visit.
- Participants who miss the 12-month visit or who do not complete any control testing at the 12-month visit, including treatment crossovers who miss or do not complete the 12-month visit, will also have their mean distance control score imputed using multiple imputation.
- To be included in the analysis, the 12-month visit must be completed no earlier than 270 days (≥ 9 months) and no later than 540 days (≤ 18 months) after randomization. If the 12-month visit is not completed within this analysis window, the distance control at 12-month visit will be imputed using multiple imputation.
- Data from participants randomized but found to be ineligible upon subsequent review of enrollment data will be included in the primary analysis.

The multiple imputation will be performed for missing data using Monte Carlo Markov Chain (MCMC) modeling. (See Section 2.4 below for further details.)

In April 2017, 28 participants were found to be incorrectly randomized because the wrong row from the randomization schedule was selected due to a programming error on the study website. (A list of these 28 participants is given in the Appendix of this analysis plan.) 20 of these 28 participants were randomized to the treatment group opposite the one they should have been randomized to if the correct row from the randomization schedule had been selected. 8 of the 28 participants were randomized to the correct treatment group by chance even though the incorrect record of the randomization schedule was chosen. As was approved by the DSMC, all 28 participants were continued in the (incorrectly) assigned treatment group (as recorded in tblPtRoster) and will be analyzed in that assigned treatment group.

115
116
117
118
119
120
121
122
123
124
125
126
127
128
129
130
131
132
133
134
135
136
137
138
139
140
141
142
143
144
145
146
147
148
149
150
151
152
153
154
155
156
157
158
159
160

2.1.2. Sensitivity Analysis

The following sensitivity analyses will be performed using the imputed dataset from the primary analysis unless otherwise specified.

2.1.3. Sensitivity Analysis #1: Complete Case Analysis (Excluding Out-of-Window Visits)

- The observed data (NOT the imputed dataset) will be used.
- All participants who complete one or more distance control assessments at a 12-month visit occurring between 9 to 18 months from randomization, including treatment crossovers and participants who are prescribed IXT treatment other than overminus or non-overminus spectacles, will have their observed 12-month data analyzed.
- Participants who miss the 12-month visit entirely or who do not complete any control testing at the 12-month visit will be excluded from the analysis.
- Participants who had the 12-month visit completed outside of the analysis window (<9 months or >18 months from randomization) will be excluded from the analysis.

2.1.4. Sensitivity Analysis #2: Complete Case Analysis (Including Out-of-Window Visits)

- The observed data (NOT the imputed dataset) will be used.
- Repeat sensitivity analysis in Section 2.2.1 above but *including* participants who had the 12-month visit completed outside of the analysis window (< 9 months or >18 months from randomization).

2.1.5. Sensitivity Analysis #3: Last Observation Carried Forward (LOCF) for Participants Starting Non-Study Treatment and Participants with Treatment Crossover

- Participants who are prescribed IXT treatment other than overminus or non-overminus spectacles for any reason at any time before the 12-month visit will have their mean distance control score from the last visit prior to starting non-study treatment for IXT carried forward as their mean distance control score at 12 months.
- Participants who switched from overminus to non-overminus treatment (or vice versa) before the 12-month visit will have their mean distance control score from the last visit prior to the treatment crossover carried forward as their mean distance control score at 12 months.
- Otherwise, data will be analyzed as in the primary analysis.

2.1.6. Sensitivity Analysis #4: Multiple Imputation for Participants with Treatment Crossover

- Participants who switched from overminus to non-overminus treatment (or vice versa) for any reason at any time before the 12-month visit will have their 12-month mean distance control score imputed using their mean control score from each of the follow-up visits before the treatment crossover occurred.
- Otherwise, data will be analyzed as in the primary analysis.

161 **2.1.7. Sensitivity Analysis #5: Additional Adjustment Factors**

- 162 • The primary analysis (a two-sided comparison of mean 12-month control of the
163 distance exodeviation between the treatment groups using an ANCOVA model)
164 will be repeated but will adjust for the following additional 4 factors: distance and
165 near PACT and near stereoacuity. The model will adjust for these factors in
166 addition to the initial baseline factors: distance control, distance PACT, age, and
167 refractive error. The treatment group difference (overminus – non-overminus) and
168 corresponding 95% confidence interval and p-value will be calculated.
169

170 **2.1.8. Interim Analysis Summary**

171 An interim monitoring plan has been developed to monitor for futility during the study.

172 The interim monitoring plan is located at:

173 F:\user\PEDIG\Studies\IXT\IXT5\Sample Size – Statistical Analysis\Statistical Analysis
174 Plan\IXT5 SAP RW\Interim Monitoring\IXT5 Interim Monitoring Plan 11-10-17 (Final
175 with Signatures).pdf
176

177 According to the IXT5 Interim Monitoring Plan, the DSMC may terminate the study
178 early:

- 179 • If the treatment effect of overminus is not found to be statistically significant
180 based on the partial 12-month data at the interim analysis stage, to be conducted
181 when approximately 50% of the participants have completed 12 months of follow
182 up.

183 OR

- 184 • If the treatment effect of overminus is not found to be statistically significant
185 based on the analysis of complete 12-month data, to be conducted when all
186 participants have completed 12 months of follow up (or have dropped from the
187 study).

188 If the study is terminated early based on the analysis of partial or complete 12-month
189 data, no further 15-month or 18-month visits will be required. The subsequent analyses
190 involving 15-month and 18-month data outlined in this SAP will be descriptive only, with
191 no statistical testing. The analyses involving 12-month data will be conducted using
192 available 12-month outcome data in accordance with the specifications laid out in this
193 SAP.
194

195 **2.1.9. Multiple Imputation of Missing Values**

196 The multiple imputation will be performed for missing data using Monte Carlo Markov
197 Chain (MCMC) modeling, which includes the mean distance control scores at all follow-
198 up visits prior to and including the 12-month visit, and the following baseline factors:
199 distance PACT, age, and refractive error. The mean distance control score will be used in
200 the MCMC model when multiple baseline measurements are available. The multiple
201 imputation will be performed separately by treatment group to account for potential
202 interaction between the treatment groups and the follow-up distance control scores. The
203 number of imputations will be set to 100. For the participants who started IXT treatment
204 other than overminus or non-overminus spectacles, only data from the visits prior to
205 starting such treatment will be used in the MCMC model. Missing baseline data are not
206 expected for distance PACT, age, and refractive error; however, if such missing data

207 occurs, it will be imputed in the MCMC model so that participants with such missing
208 baseline data are included in the analysis.

209

210 If the study is not terminated early based on partial or complete 12-month data (as
211 specified in Section 2.3), the missing mean distance control scores at all follow-up visits
212 (including 15-month and 18-month visits) will be imputed again using an MCMC model
213 that includes mean distance control scores at all follow-up visits prior to and including
214 the 18-month visit, following the same principles specified above for the imputation of
215 primary outcome at 12 months. Both the primary analysis for the 12-month outcome
216 specified in Section 2 (including sensitivity analyses) and the secondary analysis for the
217 18-month outcome outlined in this SAP will be conducted using this newly imputed
218 dataset and the results will be used in the final manuscript.

219

220

221 **2.2 Secondary Analysis: Efficacy of Overminus After Treatment Discontinuation** 222 **(18 Months, Off-Treatment)**

223

224 The analyses specified in the secondary analysis will be performed on the full cohort
225 which includes participants who were and were not prescribed full treatment between 0 to
226 12 months and weaning of overminus between 12 to 15 months. The full cohort analysis
227 will be considered the main secondary analysis. In addition, these analyses will be
228 repeated for the 18-month visit in a sensitivity analysis that will be limited to participants
229 who were prescribed full treatment and weaning, defined as those who completed their
230 15-month visit before Protocol Amendment II discontinuing overminus treatment was
231 approved by the Jaeb IRB on 12/18/19.. If retention of an on-treatment effect is stronger
232 in participants who have full treatment/weaning vs. less than full treatment/weaning, the
233 18-month treatment effect could be diluted in the full cohort analysis vs. the limited
234 cohort.

235

236 **2.2.1 Treatment Group Comparison of Mean 18-month Distance Control**

237 The analyses specified above in Section 2.1 will be repeated using the mean 18-month
238 distance control score. As per the rationale in protocol change #2 of Protocol Amendment
239 I, the 18-month comparison is a secondary analysis, hence no adjustment to alpha (5%)
240 will be made to either the primary or the secondary analyses. It is acknowledged this
241 could inflate the overall type I error rate, i.e. probability of one or more false positive
242 findings, for the analyses of these outcomes.

243

244 The treatment group comparison of mean distance control at the 18-month visit will
245 follow the same modified intention-to-treat principle as specified in Section 2.1.1. To be
246 included in the analysis, the 18-month visit must be completed no earlier than 15 months
247 and no later than 24 months after randomization. If the 18-month visit is not completed
248 within the analysis window, the distance control at the 18-month visit will be imputed
249 using multiple imputation (as specified in Section 2.1.9 above). Eighteen-month data for
250 participants in the overminus group who do not discontinue overminus spectacles
251 according to protocol will be included in analyses and will not be imputed, as will 18-
252 month data from participants in the non-overminus group who start overminus.

253
254
255
256
257
258
259
260
261
262
263
264
265
266
267
268
269
270
271
272
273
274
275
276
277
278
279
280
281
282
283
284
285
286
287
288
289
290
291
292
293
294
295
296
297
298

2.3 Exploratory Analysis: Evaluate the Effect of Weaning

To evaluate the effect of weaning, the mean change in distance control score will be compared between the following visits within the overminus group using a paired t-test if the distribution is normal, or using a Wilcoxon signed rank test if the distribution is not normal:

- From 12-month visit to 15-month visit to assess change between full strength overminus treatment (-2.50 D) to half-strength (-1.25D) overminus treatment
- From 15-month visit to 18-month visit to assess 3 months of discontinuation of overminus treatment from half-strength (-1.25D) overminus treatment
- From 12-month visit to 18-month visit to assess a 6-month weaning strategy consisting of 3 months of half-strength (-1.25D) overminus treatment followed by 3 months discontinuation of overminus treatment

This analysis will be limited to participants who were prescribed weaning when the original protocol mandated it (i.e., prior to Protocol Amendment II which discontinued weaning). In addition, to be included in the analysis, the 15-month visit must be completed no earlier than 12 months and no later than 21 months after randomization. The imputed dataset specified in Section 2.1.9 will be used in all analyses outlined in Section 2.3.

Absolute treatment effect will be estimated by calculating retention of the 12-month on-treatment effect at 18 months (off-treatment). This will be done using an ANCOVA model that adjusts for the same covariates as the primary analysis (section 2.1), in addition to time, and the interaction between treatment group and time. A percentage estimating the treatment effect retained at 18 months will be reported from the model, as well as a 95% confidence interval.

3. Objective II: Effect of Overminus Treatment on Deterioration of IXT

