2.6.2 Treatment for Non-Overminus Group

NOTE: Details of spectacles to be prescribed will be automatically calculated by the study website.

No IXT treatment other than the study spectacles specified below can be prescribed at any time during the study unless the subject meets deterioration criteria described in section 3.7.

Enrollment Visit

- Subjects in the non-overminus group will be prescribed spectacles based on the cycloplegic refraction as follows:
 - If the cycloplegic refraction is spherical and between plano sphere and +1.00D sphere in both eyes (with no astigmatism and no anisometropia), subjects will wear spectacles with plano lenses in both eyes to maintain masking.
 - Otherwise, fully correct the astigmatism and prescribe sphere as follows:
 - If least hyperopic eye has SE myopia:
 - Prescribe the full sphere in both eyes
 - If least hyperopic eye has SE hyperopia or emmetropia:
 - Prescribe sphere so that spectacles will have plano SE in the least hyperopic eye
 - Match any reduction of sphere made to the least hyperopic eye in the fellow eye
- Subjects will wear the new prescription all waking hours until the 12-month visit.

12-Month Visit*

- Spectacles will be updated at the 12- month visit using the same prescribing guidelines at enrollment (see above) but using the 12-month cycloplegic refraction, unless the subject has already met deterioration criteria confirmed by masked examiner as described in *section 3.7* in which case spectacles are prescribed at investigator discretion.
- To maintain masking, lenses will be replaced even if there is no change in the cycloplegic refraction.

* Unless the subject has already met deterioration criteria confirmed by masked examiner as described in section 3.7 in which case spectacles are prescribed at investigator discretion.

15-Month Visit*

- If the 12-month spectacles for a subject were issued **before** Protocol Amendment II, the non-overminus lenses should be replaced at the 15-month visit to maintain masking of treatment groups (see 12-month prescribing above).
- If the 12-month spectacles for a subject were issued **on/after** Protocol Amendment II and therefore are already non-overminus spectacles, the non-overminus spectacles should be continued at the 15-month visit.) There is no longer a reason to change the

1255	glasses to maintain masking, because both treatment groups are already wearing non-
1256	overminus glasses.

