3.3.1 Masked Examiner Testing

A masked examiner will assess the following at the 6-month, 12-month, 15-month, and 18-month visits regardless of whether or not the subject has already met deterioration criteria confirmed by masked examiner as described in *section 3.7* at a previous visit:

- Control assessment #1
- Stereoacuity
- Control assessment #2
- Cover test
- 1327 PACT
 - Control assessment #3
 - Assessment of deviation throughout the exam

The Masked Examiner must not verify the spectacles using lensometry, discuss compliance of spectacle wear with the subject or parents, or administer the symptom survey. The Masked Examiner should not review the subject's medical record prior to the exam.

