576 Of the 355 expected 18-month visits (as of 11/5/19), approximately 283 participants
577 (80%) will have completed a full 3-months of prescribed weaning before discontinuing
578 overminus (or non-overminus); approximately 35 to 54 (20% to 25%) participants will
579 have completed partial weaning, and approximately 18 to 37 participants (5% to 10%) are
580 expected to have no weaning at all per Protocol Amendment II. The summary statistics
581 for distribution of 18-month distance control and change from baseline in distance control
582 will be tabulated according to treatment group and whether full, partial, or no prescribed
583 weaning.

584

585 **4.2.3 Participants with Baseline Control of 3 to 5 Points (Spontaneous Tropia)**

586 Participants with baseline distance control of 3 to 5 points may have a better likelihood of
587 improving ≥ 2 points. The mean distance control of these participants is indicative of the
588 presence of spontaneous tropia on at least one of the 3 control measures, while
589 participants with mean distance control scores of 2 to <3 points had a phoria on one or
590 more of the control measures.

591

592 If there is no evidence of a treatment effect in the subgroup of participants with mean
593 distance control scores at baseline of 2 to <3 points (from Section 4.2.1), the distance
594 control primary analysis (Section 2, excluding sensitivity analysis) and secondary
595 analysis (Section 2.3) will be repeated in exploratory analyses limited to the cohort of
596 participants with baseline distance control of 3 to 5 points. This will be done at both the
597 12-month and 18-month time points.

598

599 [Note: this is included in the SAP only because it appeared in the Protocol. It is
600 recognized that in the event this analysis is carried out as specified, strict control over the
601 type I error rate will have been lost.]

602

603

604 **4.3 Safety Analyses**

605

606 **4.3.1 Refractive Error at 12 and 18 Months**

607 The proportion of participants with >1 D increase in myopia or in hyperopia from
608 baseline to 12 months and from baseline to 18 months will be tabulated separately by
609 direction of change (myopic or hyperopic), and treatment group, for refractive error as
610 measured by subjective refraction or retinoscopy and also for refractive error as measured
611 by autorefraction. The risk ratio for myopia progression of >1 D will be calculated for the

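### SAP 2.3 judges the 12–15 and 15–18 month weaning steps by change in the overminus arm alone, although the randomised control arm was scored at the same visits

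*SAP*

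**What the plan says.** SAP 2.3 states: "To evaluate the effect of weaning, the mean change in distance control score will be compared between the following visits within the overminus group". Three spans are listed: 12–15 months (full to half strength), 15–18 months (half strength to none) and 12–18 months (both steps). Each is tested by paired t-test, or by Wilcoxon signed rank test if the changes are not normal. The analysis is limited to children prescribed weaning before Protocol Amendment II and uses the imputed dataset.

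The section then adds an ANCOVA with time and treatment-by-time terms, to report the percentage of the 12-month effect retained at 18 months. That gives a between-arm view of 12–18 months, so that span is not in question here.

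The one-arm choice was deliberate. The revision history for SAP version 2.0 records that the "effect of weaning will only be calculated in the overminus group and will not use ANCOVA". It gives no reason.

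**The concern.** Distance control can change over three months for reasons unrelated to the lenses: natural course, ageing, or repeated testing. Within one arm these are added to any effect of the lens step. Higher scores mean worse control. Worsening shared by both arms would therefore look like loss from weaning, and shared improvement would hide a real loss.

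The stake is modest but real. Protocol Amendment I (rationale for change #2) says the weaning schedule may need refinement, and these stepwise results are what a reader would use to decide which step loses the effect. No trial objective rests on them.

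**Working it through.** **Is a concurrent control available?** Yes.

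- Protocol 3.3.1: "A masked examiner will assess the following at the 6-month, 12-month, 15-month, and 18-month visits". The list includes all three control assessments and is not restricted by arm.
- SAP 2.1.9 imputes missing 15- and 18-month scores, separately by treatment group, so both arms are covered.
- SAP 4.2.2 applies weaning status to overminus and non-overminus children alike, so the cohort restriction can be applied to both arms.
- Protocol 2.6.2, for 12-month spectacles issued before Amendment II: "non-overminus lenses should be replaced at the 15-month visit to maintain masking of treatment groups". Lenses were also replaced at 12 months, so receiving new lenses is matched across arms.

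**Is either step compared between arms elsewhere?** Not in the text available. SAP 2.1 and 2.2 compare arms at 12 and 18 months. SAP 4.2.2 tabulates 18-month control only. The retention model in SAP 2.3 reports 18-month retention only.

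**How far could shared drift mislead?** SAP 2.3 states no sample size or power, so there is no figure of its own to reproduce. The inputs are:

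- *Cohort.* SAP 4.2.2: "Of the 355 expected 18-month visits (as of 11/5/19), approximately 283 participants" were expected to complete full weaning, both arms together, with a further 35 to 54 partly weaned. An even split is assumed: 283/2 ≈ 141 per arm, or (283 + 54)/2 ≈ 168 if all the partly weaned are included.
- *SD of change.* Not given for a 3-month step. Three values are used:
  - 0.926, the test-retest SD in Protocol 1.13. This is measurement noise only, so rejection rates based on it are an upper bound.
  - 1.8, the planning SD in Protocol 5.7.1, taken directly as an SD of change.
  - 1.8 × √(2 × (1 − 0.25)) = 2.20, using the pilot's baseline to 8-week correlation of 0.25.
- *Drift.* Not given. The value 0.058 is the size of the test-retest shift in Protocol 1.13. It is not a time trend and serves only as a reference point. The value 0.2 is an assumption.

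With no weaning effect and shared drift δ, the paired t statistic has noncentrality δ√n/SD on n − 1 degrees of freedom. For δ = 0.2, SD = 1.8 and n = 141 this is 0.2 × √141/1.8 = 1.32, and the two-sided 5% test rejects 25.9% of the time.

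| SD of change | n per arm | Rejection at δ = 0.058 | Rejection at δ = 0.2 | δ giving 10% rejection |
|---|---|---|---|---|
| 0.926 | 141 | 11.4% | 72.1% | 0.051 |
| 0.926 | 168 | 12.7% | 79.5% | 0.047 |
| 1.8 | 141 | 6.7% | 25.9% | 0.100 |
| 1.8 | 168 | 7.0% | 29.9% | 0.091 |
| 2.20 | 141 | 6.1% | 18.8% | 0.122 |
| 2.20 | 168 | 6.3% | 21.5% | 0.112 |

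In 20,000 simulated trials per case with the same drift in both arms, a two-sample t-test on change rejected 4.7–5.3% of the time.

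**What does the control cost in precision?** The 95% half-width is 1.96 × SD/√n for one arm and 1.96 × SD × √(2/n) for the between-arm contrast, a ratio of √2 ≈ 1.41.

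| SD of change | n = 141: one arm → between arms | n = 168: one arm → between arms |
|---|---|---|
| 0.926 | 0.15 → 0.22 | 0.14 → 0.20 |
| 1.8 | 0.30 → 0.42 | 0.27 → 0.38 |
| 2.20 | 0.36 → 0.51 | 0.33 → 0.47 |

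**The case against.** - **The main off-treatment question is already randomised.** SAP 2.2 compares arms at 18 months and repeats this in the weaned cohort, and SAP 2.3 adds the retention estimate. What is left is how the loss divides at 15 months, in an exploratory section with no decision rule, for a schedule that Amendment II has ended. This stands, and it limits the importance of the point.
- **The drift is hypothetical and may be negligible.** At 0.02 to 0.03 points the one-arm rejection rate is only 5.1–5.5% (SD 1.8 to 2.20) or 5.7–7.0% (SD 0.926). This also stands: the tables show sensitivity to drift and do not show that drift occurred. But nothing in the plan shows that drift is small, and the control arm is the way to find out.
- **The 4.7–5.3% result follows from the set-up.** Identical drift was simulated in both arms, with a simple t-test on change and not the full model proposed below. That is true. Removing shared change is exactly what the contrast is for.
- **The contrast still does not test weaning against abrupt stopping.** Correct, because weaning was not randomised. It estimates how much of the treatment effect is lost at each step.
- **The existing model might already cover 15 months.** SAP 2.3 does not list the levels of time, but the only output it specifies is retention at 18 months. The SAP text between the safety section and Section 5.2.1 was not available. It is an unlikely place for this analysis.

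None of this makes a one-arm before-after test able to attribute a change to the lens step.

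**Conclusion.** The concern holds, for the 12–15 and 15–18 month steps only. As specified, the paired p-values do not measure an effect of weaning. They measure that effect plus whatever change both arms share. The size is unknown. At an SD of change of 1.8 to 2.20, a shared drift of about 0.09 to 0.12 points doubles the false-positive rate to 10%. At the noise-only SD of 0.926, about 0.05 points does so. These figures rest on an even split between arms, the assumed SDs of change and a drift equal in both arms. The change is worth making because it is cheap, but nothing confirmatory depends on it.

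**What to change.** In SAP 2.3, keep the restriction to children prescribed weaning before Amendment II, but apply it to both arms. Fit a repeated-measures model to the 12-, 15- and 18-month distance control scores with the primary-analysis covariates, treatment-by-visit terms and an unstructured within-child covariance. Report the between-arm difference in change, with its 95% confidence interval, for 12–15 and for 15–18 months as the loss of treatment effect at that step. Pool over the 100 imputations by Rubin's rules. Keep the within-arm changes as description, without attributing them to weaning, and state that the analysis does not compare weaning with abrupt stopping.

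The cost is SAP wording and analysis code, with no new data. Precision falls, for example from a half-width of 0.30 to 0.42 points at SD 1.8 and 141 per arm. SAP version 2.2 is dated February 2021, while the last 12-month visits were planned for December 2019. The 18-month visits were therefore probably complete, and the added contrasts should be labelled as specified after that version.
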